9.2.1 Treatment Assignment Procedures

Enrolled dyads will be randomized prior to the scheduling phone call using computer-generated random numbers to either the intervention group or the delayed intervention group. The intervention group will then be scheduled to have the pharmacist telehealth visit immediately (within 4 weeks) after enrollment. The delayed intervention group will be scheduled to receive the pharmacist-led component 3-4 months after enrollment. For dyads randomized to the delayed group, the project assistant will say, "I will call you in about 3 months to remind you of your appointment with the pharmacist." Due to the nature of the intervention, participants, pharmacists and PCPs cannot be masked. Project assistants will enter data into a REDCap database so that the researchers can analyze it without having access to group assignment.

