- 2a) To determine the feasibility of measuring the primary outcome, the patient-level Medication Regimen Complexity Index (pMRCI)¹⁻⁴, within the existing EHR systems, and to compare it with a more pragmatic measure, chronic medication count, as the primary outcome measure for the ePCT.
- 2b) To determine the feasibility of measuring the secondary outcome, the Family Caregiver Medication Administration Hassles Scale (FCMAHS)⁵, a caregiver-reported outcome measure.

Design and Outcomes

This is a pilot study of a pragmatic intervention consisting of the following strategies: 1) direct-to-consumer deprescribing educational materials designed to activate the care partner and PLWD; 2) a telehealth visit in which a clinical pharmacist discusses benefits and harms of the patient's medications with the patient and care partner in the context of their goals and preferences; and 3) pharmacist-PCP communication in which the pharmacist provides tailored deprescribing recommendations designed to be useful and actionable for the PCP. The study will assess the feasibility and preliminary efficacy of the intervention in two healthcare systems, to guide the subsequent evaluation of the intervention in an ePCT.

Patient eligibility criteria will be: age ≥ 65 years with a diagnosis of Alzheimer's disease or related dementia (ADRD) from ICD-9 or ICD-10 visit codes or from the electronic health record (EHR) problem list and ≥ 5 chronic medications. Patients and care partners will be enrolled as dyads and randomized to the intervention group and a delayed intervention control group that will receive the pharmacist-led component 3 months after the educational mailing.

Interventions and Duration

Dyads at each pilot site will be randomly assigned to receive the pharmacist-led intervention immediately after the educational mailing or to a delayed intervention control group that will receive the pharmacist-led component 3 months after the mailing. Piloting with a delayed intervention control group will allow for a more realistic examination of the differential effect of a low-touch control arm (educational mailing only) vs. the pharmacist-led process. Each participant will be on study (intervention period and additional follow-up) for 3 months.

Sample Size and Population

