The eligible patient population for the pilot study will be all patients at the two pilot clinics who are age 65 or greater with a diagnosis of Alzheimer's disease and related dementias (ADRD) from either ICD visit codes or documentation on the problem list. Patients must also be taking 5 or more chronic medications, and active patients, defined as having ≥ 1 visit to the primary care clinic within the past year. We will enroll 60 patient-care partner dyads (15 dyads per arm at each site).

STUDY TEAM ROSTER

Principal Investigator:	[name], MPH, PhD Johns Hopkins University School of Medicine [name] [contact] [contact] [contact]
Co-Investigators:	[name], MS Institute for Health Research, Kaiser Permanente Colorado [name] [contact] [contact] [contact] Site Principal Investigator, Kaiser Permanente
	[name], MPH Johns Hopkins University School of Medicine [name] [contact] [contact] [contact] Co-Investigator
	[name] Johns Hopkins Bloomberg School of Public Health [name] [contact] [contact] [contact] Co-Investigator
	[name] Johns Hopkins Center on Aging and Health [name] [contact] [contact] [contact] Co-Investigator, Statistician
	[name], MSPH Institute for Health Research, Kaiser Permanente Colorado

[name] [contact] [contact] [contact] Co-Investigator

PARTICIPATING STUDY SITES

[name], MPH, PhD

Johns Hopkins University School of Medicine [name] [contact] [contact] [contact]

[name], MS

Institute for Health Research, Kaiser Permanente Colorado [name] [contact] [contact] [contact]

1 STUDY OBJECTIVES

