4.3 Study Enrollment Procedures

1) Using clinical and claims data under a waiver of HIPAA Authorization, the data analytics team at each institution will identify all patients at each of the two clinics who meet inclusion criteria. This list will be routed to the project assistant via a HIPAA-compliant method.

2) The project assistant will perform administrative roles for the study. This includes: Mailing study materials with opt-out provisions to the homes of 30 randomly selected patients from this list. Patients will be entered into a study database for tracking and to avoid repeated mailings. Study materials will include a phone number that patients or care partners can call to opt out. We will continue mailing materials to eligible patients until 30 have been recruited at each clinic. Materials will also provide dyads the opportunity to opt *in* by calling the phone number. To emphasize that the study is for care partners, the envelope and introductory letter will be addressed to the patient and family (eg, "[name] and family").

Scheduling virtual visits with the clinical pharmacist. Dyads who do not opt out (and those who opt in) within 14 days of the study mailing will be randomized using computer-generated random numbers to either the intervention group or the delayed intervention control group, and called by the project assistant.

If the patient and care partner do not opt out, the project assistant will call the patient's phone number listed in the EHR and use an IRB-approved script (attached) to identify the care partner:

- The project assistant will briefly explain that they are calling about "a program for family members and friends who are caring for someone with memory problems."
 - If the patient answers the phone, the project assistant will say, "I'm calling about your medicines. Many people have someone who helps them manage their medicines on a daily basis." They will then ask to speak with the care partner.
 - If the care partner answers the phone, the project assistant will ask, "Are you the person who helps [PATIENT] the most to manage their medicines?"

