9.2 Sample Size and Randomization

Sample size calculation: With an attrition rate of 10%, a sample size of 30 dyads per arm will produce a 2-sided 95% confidence interval with a width equal to 0.4 standard deviation (SD) when the SD of the study outcome (ie, based on normalized score) is 1.

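### The protocol fixes 15 dyads per arm at each site but specifies no restriction or site stratification that would produce this, and the arm models do not adjust for site

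*Combined protocol and SAP*

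**What the plan says.** The Précis (Sample Size and Population) sets the counts: "We will enroll 60 patient-care partner dyads (15 dyads per arm at each site". Section 3 repeats them. Section 4.3 recruits to 30 per clinic: "We will continue mailing materials to eligible patients until 30 have been recruited at each clinic". Section 9.2 bases its precision statement on "a sample size of 30 dyads per arm".

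The method of allocation is described in three places. Section 9.2.1, the section devoted to it, says dyads are randomised "using computer-generated random numbers to either the intervention group or the delayed intervention group". Section 4.3 says they "will be randomized using computer-generated random numbers to either the intervention group or the delayed intervention control group", and Section 6.2.2 is to the same effect. None of them gives an allocation ratio, blocks, strata, a fixed-count list or a concealment method. The Précis (Interventions and Duration) and Section 3 add where assignment takes place: "Dyads at each pilot site will be randomly assigned to receive the pharmacist-led intervention immediately after the educational mailing".

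Randomisation comes before the scheduling call. At that call dyads may still decline, or be excluded if no care partner can be identified (Sections 4.3 and 6.2.1).

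In Sections 9.1 and 9.5, the pMRCI change score is regressed on arm, and health system enters only through robust standard errors. The FCMAHS model is a regression of change on arm, with no mention of site.

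**The concern.** A fixed count in each site-by-arm cell is a property of a restricted randomisation. The text states the count without the restriction, so the allocation cannot be reproduced from the protocol, and under one natural reading the planned split would rarely occur.

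Site matters because there are only two systems and they supply medication data differently: the EHR at one and the Virtual Data Warehouse at the other (Sections 6.2 and 10.2). Section 6.2 also says that methods for identifying chronic medications in the Johns Hopkins EHR are still under examination. If 3-month change differs between systems and the arms end up with different site mixes, part of that difference enters the arm estimate. Robust standard errors change the stated uncertainty but not the estimate. Sections 9.1 and 9.5 intend the pilot's estimates to inform planning of the larger trial.

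**Working it through.** **Inputs.** 15 per arm per site and 60 in total (Précis, Section 3); 30 per clinic (Section 4.3); 30 per arm and 10% attrition (Section 9.2), so 27 evaluable per arm; outcome SD of 1 (Section 9.2). A 1:1 ratio is implied by equal arms but not stated.

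**The plan's own count.** 15 × 2 arms × 2 sites = 60, which agrees with 30 per clinic and 30 per arm. The target is internally consistent.

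**Chance of the stated split under different readings**

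| Reading of the allocation | 15/15 at one site | 15/15 at both |
|---|---|---|
| Simple 1:1, with or without a separate list per site | C(30,15)/2^30 = 0.144 | 0.144² = 0.021 |
| One list forced to 30:30, not stratified | 0.203 | C(30,15)²/C(60,30) = 0.203 |
| Site-stratified blocks of a size dividing 30 (2, 6 or 10) | 1 | 1 |
| Site-stratified blocks of 4 | 4/6 = 0.667 | 0.444 |

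In the second row the two columns are equal because 15 at one site forces 15 at the other. In the last row the final block is incomplete at 30. The last two rows count randomised dyads before any are lost.

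**Imbalance under simple allocation**
- A site at 10:20 or worse: 2 × P(Bin(30, 0.5) ≤ 10) = 0.099.
- Total arms at 25:35 or worse: 2 × P(Bin(60, 0.5) ≤ 25) = 0.245.
- Site-mix gap. With a and b intervention dyads at sites 1 and 2, the gap in site 1's share between arms is a/(a+b) − (30−a)/(60−a−b). For example, a = 18 and b = 12 give 0.60 − 0.40 = 0.20. Exact enumeration over both binomials gives P(|gap| ≥ 0.20) = 0.155 and a root-mean-square gap of 0.131.

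**Cost in precision.** The SE ratio against 30:30 at 25:35 is √[(1/25 + 1/35)/(2/30)] = 1.014. For a single site at 10:20 against 15:15 it is √[(1/10 + 1/20)/(2/15)] = 1.061.

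**Shift in the unadjusted arm effect.** Shift = gap × D, where D is the between-system difference in mean 3-month change. The documents do not give D, so a range is assumed:

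| Assumed D (SD) | Root-mean-square shift (0.131 × D) | Shift at a gap of 0.20 |
|---|---|---|
| 0.10 | 0.013 | 0.02 |
| 0.25 | 0.033 | 0.05 |
| 0.50 | 0.066 | 0.10 |
| 1.00 | 0.131 | 0.20 |

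For scale, the SE of the arm difference with 27 per arm is √(2/27) = 0.272 SD.

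**Losses after randomisation.** The documents give no rate for dyads lost between randomisation and recruitment. With assumed losses of 10% to 50%, replaced until 30 are recruited, simulated site-stratified blocks of 2 or 6 give exactly 15/15 at a site with probability about 0.44 down to 0.20. They stay within 2 of 15 with probability about 0.99 down to 0.79. Simple allocation stays within 2 of 15 with probability 0.638.

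**The case against.** A reader might infer that the trial uses plain randomisation with no strata or blocks. The documents do not support that. Computer-generated numbers name the source of randomness, and a permuted-block list is also computer-generated. The wording about assignment at each pilot site, together with a fixed count per cell, suggests that allocation within site may be intended. This part of the objection stands: the restriction is unstated, and the probabilities for simple allocation are conditional on that reading. The wording still supplies no restriction, and separate unblocked lists per site would give 15/15 only 14.4% of the time at each.

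A reader might also infer that the arm comparison is biased by health system. That does not follow. Any imbalance would be a chance result of randomisation, not a systematic one. The outcomes are change scores, so a constant difference between data sources cancels and only a difference in change matters. The data-source argument does not reach the FCMAHS, which is collected from care partners by telephone or web link at both sites.

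It is also fair that this is a pilot without statistical hypotheses, that the first aims are descriptive, and that unequal arms cost little precision. These points limit the consequence. They do not supply the missing method or put site into the estimate.

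Last, stratified blocking cannot guarantee 15 per cell among recruited dyads, because some can be lost after randomisation. That also stands, and is why the count should be described as a target.

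**Conclusion.** The point holds as a gap in specification with a modest consequence. The protocol commits to a count per site and arm and describes no procedure that yields it. If allocation is simple, the split is met at both sites about 2% of the time, and a site-mix gap of 20 points or more arises about 16% of the time. Precision is barely affected. The root-mean-square shift in the arm effect is about 0.13 times a between-system difference that the documents do not give. Even at an assumed 0.5 SD, that is about 0.07 SD against a standard error near 0.27 SD. The case for change rests on reproducibility and on a better method being nearly free, not on lost power or demonstrated confounding.

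**What to change.** In Sections 4.3, 6.2.2 and 9.2.1, state that dyads are randomised 1:1, stratified by site, in permuted blocks, and say how the sequence is generated. Conceal upcoming assignments from the project assistants; they must know the current dyad's arm in order to schedule the visit, so only future assignments can be hidden. Varying the block size limits predictability, but sizes of 2 and 4 cut at 30 give exactly 15/15 at only about 89% of sites in simulation. The wording should therefore not promise an exact count.

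In the Précis and Section 3, describe 15 per cell as a target, since dyads can decline or be excluded after randomisation.

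In Sections 9.1 and 9.5, add site as a fixed covariate in both the pMRCI and the FCMAHS arm models.

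The cost is one pre-generated list per site, slightly more predictable assignment, and one degree of freedom in each model. If the team already intends site-stratified blocks, the allocation part needs only a sentence.

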9.3 Interim analyses and Stopping Rules

There are no interim analysis planned or stopping rules.

9.4 Outcomes

Aim 1 is to assess the feasibility and acceptability of ALIGN in two different health care systems, to guide the subsequent evaluation of the effectiveness of the intervention in an embedded pragmatic trial. Data to measure feasibility will be acquired from the EHR, REDCap surveys completed by the pharmacists, and audiorecordings of pharmacist phone calls with care partners. We will collect the following measures:

- Proportion of dyads that opt out of the intervention;
- Proportion of pharmacist messages to the PCP that receive an acknowledgement or response;
- Number of contacts between pharmacist and PCP and between pharmacist and dyad;
- Time required by the pharmacist to complete the intervention;

Proportion of intervention elements, including pharmacist phone calls, successfully completed.
To evaluate intervention acceptability, we will track the following:

• Type of recommendations made by the pharmacist and acceptance rates for those recommendations (project assistants will review the EHR for notation of patient/care partner and PCP acceptance). The pharmacists will document each phone call with the dyad in the EHR and will record whether the patient and care partner have agreed to the recommendations. The template for the pharmacist message to the PCP (attached) includes a routing comment that asks the PCP to respond via secure chat or staff message – either to indicate acceptance or ask questions about the recommendations.

Aim 2 is to determine the feasibility of the primary and secondary outcome measures for the subsequent ePCT:

Aim 2a is to determine the feasibility of measuring the primary outcome, the patient-level Medication Regimen Complexity Index (pMRCI)¹⁻⁴, within the existing EHR systems, and to compare it with a more pragmatic measure, chronic medication count, as the primary outcome measure for the ePCT.

Aim 2b is to determine the feasibility of measuring the secondary outcome, the Family Caregiver Medication Administration Hassles Scale (FCMAHS)⁵, a caregiver-reported outcome measure.

As described in Section 6.2, we will develop the procedures for collecting the pMRCI and FCMAHS. In Aim 2a, feasibility will be measured as follows:

• Proportion of participants with data elements available vs. unavailable to calculate the pMRCI.

To compare it with chronic medication count as the primary outcome measure for the ePCT, we will measure:

- Change in chronic medication count; and
- Change in pMRCI from baseline to 3 months.

Chronic medication count will be obtained from the EHR using algorithms refined in OPTIMIZE.

In Aim 2b, feasibility will be measured as follows:

- Response rate and completion time for the FCMAHS using each mode of administration.
- Change in FCMAHS from baseline to 3 months.

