 This is the standard approach that clinic staff use to call patients with dementia on the phone and identify their care partners during the course of clinical care. As the intervention is designed to address the needs of care partners and requires their participation, the project assistant will ask to speak with the care partner first. Because some patients with mild or moderate dementia may be interested in hearing about the program, the project assistant will offer to describe it to the patient as well.
- Patients who are unwilling or unable to identify a care partner who helps them manage their medicines will be excluded. The project assistant will document the reasons for ineligibility in a REDCap Screening Log.
- The project assistant will briefly describe the pharmacist consult to the care partner. If the care partner agrees, the project assistant will schedule the pharmacist call, which will occur immediately (within 4 weeks) for the intervention group and at approximately 3 months for the delayed intervention control group.

4) If patients or care partners opt out during the phone call, the project assistant will document the reason (eg, no time to participate, not interested) in a REDCap Screening Log.

5) Dyads randomized to the delayed intervention group will be told that they will receive another phone call from the project assistant in approximately 3 months to remind them of their appointment with the clinical pharmacist.

6) After scheduling the pharmacist consult, project assistants will offer care partners in both groups the option of completing the secondary outcome measure, the Family Caregiver Medication Administration Hassles Scale (FCMAHS). For care partners who are interested in completing the FCMAHS, project assistants will obtain verbal consent when administering the measure over the phone (see script). If the care partner does not wish to complete the FCMAHS over the phone during the scheduling phone call, the project assistant will offer to call back before the pharmacist visit (up to 28 days) or to later e-mail the care partner a link to an electronic version.

5 STUDY INTERVENTIONS

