devices. We are examining different methods of identifying chronic medications in the Johns Hopkins EHR.

Patient-level Medication Regimen Complexity Index (pMRCI): Scores are derived from weighted values of regimen components (eg, dosage formulations, frequencies, and specific instructions).² We will adapt an algorithm developed and tested by [name] team to extract pre-specified variables from the EHR and calculate pMRCI scores in REDCap.²⁰ The data analytics teams at both institutions will determine the steps necessary to further adapt the pMRCI for use within the existing EHR systems. In doing so, we will build on methods developed by JHU researcher, [name], who automated the pMRCI within an EHR and calculated pMRCI scores for 70,000 patients.^{3,38} Similar EHR adaptations of the pMRCI by other researchers will also serve as a foundation for our work.¹⁰⁹

Family Caregiver Medication Administration Hassles Scale (FCMAHS): Collected from family care partners at baseline by the project assistant and again at approximately 3 months after enrollment. For care partners who are unable to complete the FCMAHS by phone, we will examine the feasibility of administering it electronically by e-mailing them a link. See attached patient intervention materials. Project assistants will record administration time when the FCMAHS is administered over the phone. Care partners will be asked to record administration time when it is self-administered electronically.

Feasibility measures:

Proportion of dyads that opt out: Will be assessed from the patient recruitment/ tracking log completed by project assistants.

Proportion of participants with data elements available to calculate pMRCI: Will be calculated based on the algorithm developed above.

Response rate and completion time for FCMAHS: Completion time will be collected by project assistants when they administer the FCMAHS on the telephone, and via self-report when it is administered electronically. The response rate using both modes of administration will be assessed.

Proportion of pharmacist messages to PCP that receive an acknowledgement or response; number of contacts between pharmacist and dyad; number of contacts between pharmacist and PCP: Project assistants will extract these data from the EHR at 3 months.

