6.2.2 Enrollment, Baseline, and/or Randomization

Enrollment

Project assistants will mail study materials with opt-out provisions to the homes of 60 patients (30 at each site). Dyads who do not opt out (or who opt in) will be called by the project assistant approximately 14 days later to describe the pharmacist consult and assess interest. Enrollment will be defined as the date of this phone call.

Baseline Assessments

The baseline point will be defined as the date of the enrollment phone call, whether or not dyads are randomized to the intervention or delayed intervention control group.

Randomization

Dyads who do not opt out (or who opt in) will be randomized to the immediate or delayed intervention group prior to the enrollment/scheduling phone call using computergenerated random numbers. The intervention group will be scheduled to have the pharmacist telehealth visit immediately (within 4 weeks) after enrollment. The delayed intervention group will receive the pharmacist-led component 3-4 months after enrollment. For dyads randomized to the delayed group, the project assistant will say, "I will call you back in about 3 months to remind you of the call with the pharmacist."

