6.2.3 Follow-up Visits

As described in the Evaluations Table, dates for follow up measurements will be relative to baseline/enrollment. This is defined as the date of the enrollment phone call. Data will be extracted from the EHR and VDW as described above. There will be one follow up call/e-mail to administer the FCMAHS 3 months after enrollment for care partners who have opted to complete it.

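### FCMAHS forms are sought only from care partners who book, opt in and stay in, all after randomization, and the response rate has no stated denominator

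*Combined protocol and SAP*

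**What the plan says.** All references are to the combined protocol and SAP.

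- **Measure.** Section 9.4 gives the Aim 2b feasibility measure as "Response rate and completion time for the FCMAHS using each mode of administration", and adds change in the Family Caregiver Medication Administration Hassles Scale (FCMAHS) from baseline to 3 months. Section 6.2 says "The response rate using both modes of administration will be assessed". Neither gives a denominator or a target.
- **Randomization and enrollment.** Under 6.2.2, dyads "will be randomized to the immediate or delayed intervention group prior to the enrollment/scheduling phone call"; 9.2.1 agrees. Section 6.2.2 also states "Enrollment will be defined as the date of this phone call".
- **Baseline offer.** Section 4.3: "After scheduling the pharmacist consult, project assistants will offer care partners in both groups the option of completing the secondary outcome measure". Sections 5.1, 6.2.1 and 11.2 give the same order.
- **3-month offer.** Section 6.2.3 provides one follow-up contact "3 months after enrollment for care partners who have opted to complete it". Section 6.2.4 adds that participants who stop the intervention early, for example by opting out during the pharmacist call, still have record data extracted but are not offered the FCMAHS.
- **Mode.** Section 6.2: "For care partners who are unable to complete the FCMAHS by phone, we will examine the feasibility of administering it electronically". Sections 4.3, 5.1 and 6.2.1 offer a call-back or a link to those who do not want to, or cannot, complete the form on the scheduling call. Section 11.2 instead lets the care partner choose phone or web.
- **Analysis.** Sections 9.1 and 9.5 adopt intention-to-treat for the comparative results of Aim 2b. They also promise to keep non-compliance with the intervention separate from non-compliance with follow-up.

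**The concern.** Whether a care partner is asked for the FCMAHS depends on three things that happen after allocation: booking the consult, opting in to the form, and not leaving the intervention. Each can differ between arms. At 3 months the rule in 6.2.4 turns non-compliance with the intervention into missing follow-up, although 9.1 and 9.5 say the two will be kept apart.

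Aim 2b is meant to tell the planners of the embedded pragmatic trial whether this caregiver-reported outcome can be collected. For that they need to know what share of randomized dyads yields a form, at each time point and in each arm. A rate without a denominator does not tell them. Nor does a pair of rates by mode when one mode is mostly offered after the other has been passed up.

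**Working it through.** The plan states no FCMAHS response rate, booking rate or split by mode, so there is no figure to reproduce. Step 1 sets the rules side by side. Steps 2 and 3 are illustrations with assumed inputs.

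**1. Who can lose the 3-month form, by arm**

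| | Immediate | Delayed |
|---|---|---|
| Pharmacist call (6.2.2) | within 4 weeks | 3-4 months |
| 3-month FCMAHS (6.1) | day 90 ± 45 | day 90 ± 45 |
| Call precedes the form? | almost always | often not |

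The form window runs from day 90 - 45 = 45 to day 90 + 45 = 135. An immediate-arm dyad that opts out during its call, by about day 28, does so before the window opens and is not offered the form. A delayed-arm dyad will often reach the form before its call, so the same behaviour costs it nothing. With 30 dyads per arm, each form withheld is 1/30 = 3.3 percentage points of that arm's 3-month rate. The documents give no rate of opting out during the call, so the total cannot be computed.

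**2. The denominator**

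Let s be the share of randomized dyads that book, c the share of booked dyads completing baseline, and f the share of baseline completers completing 3 months. All three are assumed.

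- Baseline rate among booked = c; among randomized = s × c; ratio = 1/s.
- 1/0.8 = 1.25; 1/0.5 = 2.0; 1/1.0 = 1.0 (no difference).

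Take 60 randomized, s = 0.8, c about 0.7, f about 0.8, giving 48 booked, 34 baseline forms and 27 follow-up forms:

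| Time point | Narrow denominator | All randomized |
|---|---|---|
| Baseline | 34/48 = 70.8% (95% CI 56.8-81.8) | 34/60 = 56.7% (44.1-68.4) |
| 3 months | 27/34 = 79.4% | 27/60 = 45.0% |

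The baseline contrast is the effect of booking alone (70.8/56.7 = 1.25). The 3-month contrast also contains baseline non-response. If all 60 booked, with the same c and f, it would be 34/60 = 56.7%, so only part of the gap between 79.4% and 45.0% comes from booking. Over s from 0.5 to 1.0 and c from 0.5 to 0.9, the booked-denominator rate runs from 50% to 90% and the randomized-denominator rate from 25% to 90%.

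**3. Rates by mode**

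Assume 48 care partners are offered the form, phone first.

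| Completed by phone | Link, of those left | Link, of all 48 | Either mode |
|---|---|---|---|
| 24/48 = 50% | 12/24 = 50% | 12/48 = 25% | 36/48 = 75% |
| 24/48 = 50% | 17/24 = 70.8% | 17/48 = 35.4% | 41/48 = 85.4% |
| 36/48 = 75% | 6/12 = 50% | 6/48 = 12.5% | 42/48 = 87.5% |

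The link rate can lie below, at or above the phone rate, depending on the inputs and the denominator. Only the cumulative column has one meaning throughout.

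**The case against.** Several stronger readings are tempting, and the documents do not support them.

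- **The response rate is inflated.** A reader might infer this from the offer-after-booking rule. But no denominator is stated, enrollment is the date of the call and not the booking, and Aim 2b has an intention-to-treat principle. With all randomized dyads as denominator there is no inflation. The plan permits an inflated rate; it does not commit to one.
- **The mode comparison favours phone.** No test or rule for choosing a mode is planned, 11.2 lets the care partner choose, and step 3 shows that the direction is not fixed. What stands is that mode is self-selected under every passage and sequential under most.
- **The later trial's response will be overstated.** The documents say only that it will be cluster randomized, not how its care partners will be approached. This remains a possibility.
- **Self-timing is an error.** Section 6.2 says openly that "Care partners will be asked to record administration time when it is self-administered electronically", while staff time the phone version. That is a further reason not to compare times across modes, but not a mistake.

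The best defence concerns the base of 60. Section 4.3 continues mailing until 30 are recruited at each clinic and logs refusals separately, so decliners may be replaced and booking among the final 60 may be near complete. The text leaves this open. But decliners were randomized before they declined, so replacing them is itself selection after allocation. The factor also does not change: at s = 0.8, 60 booked means 60/0.8 = 75 randomized, and 75/60 = 1.25.

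It is also fair that opt-outs and reasons are logged, so other denominators could be worked out later, and that the opt-in wording in 6.2.3 need not exclude someone who agreed but missed baseline. Neither recovers a form that was never offered. Multiple imputation is mentioned in 9.5 in the pMRCI paragraph, not the FCMAHS one. Even if it applied, 6.2.4 leaves no 3-month FCMAHS from discontinuers to inform it.

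**Conclusion.** The point holds in this form. FCMAHS collection is conditional on events after randomization. The rule withholding the 3-month form from discontinuers can fall mainly on the immediate arm, which conflicts with the intention-to-treat analysis stated for Aim 2b. That follows from the plan's own timing and needs no assumed rate; its size cannot be computed from the documents. Separately, the undefined denominator allows a reported baseline rate to exceed the randomized-dyad rate by 1/s (1.25 at an assumed 80% booked, 2.0 at 50%, nothing if all book), and rates by mode are not comparable.

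This is a pilot without statistical hypotheses, and none of this threatens its main feasibility aim. It is worth correcting because the change is small and response is one of the few results Aim 2b will produce.

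**What to change.** 1. **Sections 6.2.3 and 6.2.4.** Offer the 3-month FCMAHS to every enrolled care partner who has not refused contact, whether or not baseline was completed or the intervention was discontinued. Take verbal consent at that contact where it has not been given. State whether someone reached on the call who declines the consult counts as enrolled.
2. **Section 9.4.** Define response at each time point as forms completed over all randomized dyads with an eligible care partner, by arm and site. Show the counts randomized, reached, booked, offered and completed. List those never reached separately, since their eligibility is unknown.
3. **Section 9.4, modes.** Report modes as a cumulative sequence (scheduling call, call-back, link), with the number offered each, labelled descriptive.
4. **Sections 6.2 and 11.2.** Reconcile how mode is chosen: a link for those unable to use the phone, or free choice.

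The cost is a few more contacts, an edit to the consent script and a lower headline response rate. A 3-month form without a baseline informs response but not the observed change score. Items 2 to 4 are wording. Item 1 must be in place before the 3-month contacts are made.
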